16.4 Storage of Clinical Supplies

Acthar and placebo will be maintained in a temperature controlled, secure locked area with restricted access at the study site.

Study drug will be supplied in kits containing the appropriate amount of vials. Study drug will be stored under refrigeration between 2° to 8°C (36° to 46°F). Please refer to the Pharmacy Manual for complete information regarding storage and accountability of study drug.

16.5 Drug Accountability

In accordance with ICH requirements, the investigator will, at all times, be able to account for all study drug furnished to the study site. A drug accountability record will be maintained for this purpose. The investigator must maintain accurate records indicating dates and quantity of study drug received, to whom it was dispensed (subject-by-subject accounting) and accounts of any study drug accidentally or deliberately destroyed. All unused study drug not involved in immediate subject dosing will be maintained under locked, temperature-controlled storage at the study site.

16.6 Compliance Monitoring

Prior to beginning the administration of study drug, subjects and/or their caregiver will be trained on dosing administration and must exhibit proper technique. Subjects and/or their caregiver will be trained on the completion of the study diary and will complete study diary entries to record all study drug administration and will bring it, along with all study drug kits including used vials to each visit. Each time study drug is dispensed compliance will be encouraged. Subject diary training is an ongoing process as the diary will be reviewed with the subject at each visit to monitor compliance with study drug administration.

17 EFFICACY ASSESSMENTS AND PROCEDURES

Efficacy assessments will be evaluated at times specified in the Schedule of Study Events (Table 8-1). Below is a general instruction of the administration of these assessments. Specific instructions and questionnaires/forms (where appropriate) will be provided in a separate document.

17.1 Physician Completed Assessments

The SLEDAI-2K, BILAG-2004, PGA, SFI, CLASI-Activity and 28 Joint Count are assessments to be completed by the investigator or designee. When these assessments are required, they should be done immediately after subject reported outcome/questionnaire completion (if applicable) and must be completed prior to any study drug dosing.

17.1.1 Systemic Lupus Erythematosus Disease Activity Index-2000

The SLEDAI-2K is a modified version of a composite score based on the presence or absence of clinical signs, clinical symptoms, and immunologic laboratory results taken within 10 days of the evaluations ([Bombardier et al, 1992](#); [Gladman et al, 2002](#)). Disease activity is based on 24 questions weighted across 9 organ systems with total scores ranging from 0 to 105 but are generally < 20 with very active disease. The Clinical SLEDAI-2K score is derived without the inclusion of points attributed to laboratory test results.

17.1.2 British Isles Lupus Assessment Group 2004

The BILAG scores disease involvement within each organ system based upon the intent to treat premise ([Isenberg et al, 2005](#)). The major difference between the BILAG and other disease activity indices is that disease activity in different organs/systems is reported separately. Specific manifestations in 9 organ systems are scored (there are a total of 97 items). Each item is rated as 0 (not present), 1 (improving), 2 (same), 3 (worse), or 4 (new) in the last 4 weeks compared with the previous 4 weeks.

The numerical scores are used to categorize each organ system by an alphabetical score: ‘A’ reflecting severe disease requiring increases in prednisone to > 20 mg daily and/or addition of immunosuppressive agents, ‘B’ indicated less active disease, requiring low-dose prednisone and/or symptomatic treatment with NSAIDs and/or antimalarials, ‘C’ reflecting mild disease requiring only symptomatic therapy, ‘D’ reflecting previous organ system involvement without current disease activity, and ‘E’ reflecting no prior or no current disease involvement in that organ system.

[BILAG 2004](#) is a revised version of the original BILAG. The revised index removed the vasculitis section, placing individual clinical features more appropriately within the other organs or systems. It now incorporates sections on gastrointestinal disease and has an ophthalmology section, both missing from the original. Furthermore, some items related to damage were removed.

17.1.3 Physicians Global Assessment

PGA is a 100 mm visual analogue scale anchored at 0 (none) and 3 (severe) with intermediate lines at 1 (mild) and 2 (moderate). It was designed for physicians to provide an overall assessment of a patient’s wellbeing ([Petri et al, 1999](#)).

17.1.4 SELENA Flare Index

The SFI categorizes SLE flare as mild, moderate or severe based on the following 6 variables (Buyon et al, 2005):

- Change in SELENA SLEDAI score from the most recent assessment to current.
- Change in signs or symptoms of disease activity.
- Change in prednisone dosage.
- Use of new medication for disease activity or hospitalization.
- Change in PGA score.
- Hospitalization for SLE activity.

A severe flare is defined as 1 or more of the following: a) SLEDAI score greater than 12; b) new or worsening CNS involvement, vasculitis, glomerulonephritis, myositis, thrombocytopenia (platelet count < 60,000/mL), or hemolytic anemia (hemoglobin level < 70 g/L or decrease in hemoglobin level > 30 g/L), each requiring doubling of corticosteroid dosage to a final dosage > 0.5 mg/kg per day or acute hospitalization; c) any manifestation requiring an increase in dosage of prednisone or equivalent drug to greater than 0.5 mg/kg per day, or initiation of therapy with cyclophosphamide, azathioprine, mycophenolate mofetil, or methotrexate; d) hospitalization for lupus activity; and e) PGA score greater than 2.5 points.

17.1.5 Cutaneous Lupus Erythematosus Disease Area and Severity Score-Activity

The CLASI was developed to specifically track cutaneous activity and damage in SLE (Klein et al, 2010). The CLASI uses separate activity and damage scores as indicators of disease burden. The activity score reflects ongoing inflammation that can be treated, with points given for the presence of erythema, scale, mucous membrane lesions, recent hair loss, and inflammatory alopecia. The damage score represents the irreversible aftermath of inflammation. Only the CLASI activity score will be used in the study.

17.1.6 28 Joint Count

The 28 Joint Count includes assessment of swelling and tenderness in the shoulders, elbows, wrists, metacarpophalangeal joints, proximal interphalangeal joints and knees.

19.3 Current Medical Conditions

At each visit after screening, subjects will be asked about any changes in medical conditions, specifically new medical conditions and worsening of existing medical conditions. Any changes since the Screening Visit will be recorded as AEs, as appropriate.

19.4 Physical Examination

A complete physical examination will be performed at the Screening and Week 24/Early Termination Visit. The complete physical examination includes evaluation of the head, eyes, ears, nose, throat, neck (including thyroid), cardiovascular system (including assessment of heart, peripheral pulses, presence or absence of edema), lungs, abdomen (including liver and spleen, bowel sounds), lymph nodes, musculoskeletal system (including spine, joints, muscles) neurological system (including cranial nerves, reflexes, sensation, strength), skin, extremities and other conditions of note.

A limited physical examination, including evaluation of lungs, heart, abdomen, and extremities will be done at all other visits.

The findings of the physical examinations completed prior to the Randomization visit will be recorded as Medical History..

19.5 Height and Weight

Height will be collected at screening only. Weight will be collected at all visits.

19.6 Vital Signs

Vital signs will be obtained after the subject has been seated for 5 minutes (minimum) and will include systolic and diastolic blood pressures, pulse rate, respiratory rate, and body temperature. Additionally, at the Screening and Randomization Visits, blood pressure will be measured 3 times, with at least 5 minutes between assessments after the subject has been seated for a minimum of 5 minutes prior to the initial blood pressure assessment.

The investigator may perform additional unscheduled vital sign measurements to evaluate or manage a suspected AE. These unscheduled vital sign measurements should be obtained after the subject has been seated for at least 5 minutes, if possible. Unscheduled vital signs will be recorded.

The date and time for all vital sign assessments will be recorded.

Screening/Randomization

A subject with systolic blood pressure > 150 mm Hg and diastolic blood pressure > 90 mm Hg (average of 3 assessments) at the Screening or Randomization Visits does not qualify for the study.

On Study Assessments

If an on-study systolic blood pressure is > 150 mm Hg and diastolic blood pressure is > 90 mm Hg, an AE will be recorded if the investigator determines the change is clinically significant or requires a change in the subject's clinical management.

19.7 Clinical Laboratory Tests (Chemistry, Hematology and Urinalysis), HbA1c, IGRA, Direct Coombs test, Pregnancy Tests, ■■■■ ■■■■; and C3, C4, and anti-ds DNA antibodies

The clinical laboratory tests are listed in Attachment 1. All clinical laboratory tests will be done at a central laboratory facility except urine pregnancy (at the site) and ■■■■
■■■■. Specific instructions for collection, processing, storage, and shipment of clinical laboratory samples will be provided in a separate laboratory manual, where appropriate.

Samples for laboratory testing at all visits may be collected under fasted or nonfasted conditions. Fasting early morning samples are preferred, but a random daytime sample is acceptable. The date and time of the sample collection must be documented on the laboratory report. Investigators must review and sign laboratory reports. The clinical significance of each laboratory abnormality will be documented. New clinically significant laboratory abnormalities or clinically significant changes in laboratory values will be reported as AEs.

Hematology with differential, serum chemistry, and urinalysis samples will be collected at the specific times starting at screening and throughout the study.

In addition:

- All female subjects of child-bearing potential will have a serum pregnancy test at the Screening and Follow-up Visits. A positive urine test after randomization will be confirmed by a serum pregnancy test. Urine pregnancy tests will be done at other specified visits throughout the study. Results must be available prior to dosing with protocol mandated study drug. Subjects with positive results will be ineligible for study entry (Screening Visit or Randomization) or withdrawn from the study. Any

female subject that becomes pregnant during the study will be immediately withdrawn and the pregnancy reported as per [Section 21.6](#).

If applicable, the subject's agreement to use contraception throughout their study participation, and for 28 days after ending study participation, will be documented.

- A lipid panel (high density lipoprotein, low density lipoprotein, triglycerides, and total cholesterol) will be done at the Screening, Randomization, Week 12, and Week 24 Visits.
- HBsAg and HBcAb will be performed at the Screening Visit. Results of these tests must be negative or nonreactive for subjects to qualify for the study.
- HCV will be performed at the Screening Visit. A positive HCV will automatically trigger a HCV PCR analysis. HCV PCR must be < 25 IU/mL to qualify for the study.
- IGRA for TB will be performed at the Screening Visit. Results of this test must be negative for subjects to qualify for the study.
- HbA1c will be performed at the Screening Visit. HbA1c must be $\leq 6.5\%$ for subjects to qualify for the study. Additional HbA1c tests will be done at specified times during the protocol.

■ [REDACTED]
[REDACTED]

- C3, C4, and anti-ds DNA antibody samples will be taken at specified times during the study. -

Out-of-Range Laboratory Values

Laboratory values from samples collected at the Screening Visit will be evaluated by the investigator for eligibility of the subject in the study. Clinical laboratory tests may be repeated once to determine subject eligibility.

Laboratory values that fall outside the reference range from samples collected at the Randomization Visit and throughout the study will be assessed by the investigator for clinical significance. If the out of range value is deemed clinically significant by the investigator, an AE will be recorded.

All data will be summarized by treatment groups as appropriate. Data summary and analyses will be performed with SAS 9.2 or higher.

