13 SELECTION OF SUBJECTS

13.1 Inclusion Criteria

Subjects must meet all of the following criteria for inclusion in the study at the Screening Visit and the Randomization Visit.

1. Subjects must be adequately informed and understand the nature and risks of the study and must be able to provide a signature and date on the ICF.
2. Subjects must be ≥ 18 years of age at Screening Visit and can be male or female.
3. Female subjects must be of nonchildbearing potential (history of hysterectomy, bilateral oophorectomy, or bilateral tubal ligation; or postmenopausal with no history of menstrual flow in the 12 months prior to the Screening Visit); or if of childbearing potential must be nonpregnant, nonlactating and agree to use effective contraception when with a male partner throughout study participation (through the Follow-up Visit). Acceptable forms of contraception include hormonal measures (oral contraceptive pills, contraceptive patch, contraceptive ring, injections), intrauterine devices, double barrier method (condom plus diaphragm, condom or diaphragm plus spermicidal gel or foam), and abstinence.
4. Male subjects with a female partner of childbearing potential must have been surgically sterilized (vasectomy) or agree to use a double barrier for contraception (condom plus

- diaphragm, condom or diaphragm plus spermicidal gel or foam) or remain abstinent throughout their study participation (through the Follow-up Visit).
5. Subjects must have a diagnosis of SLE according to the American College of Rheumatology revised criteria (fulfilled ≥ 4 criteria) ([Hochberg, 1997](#); [Tan et al, 1982](#)).
 6. Subjects must have active SLE as demonstrated by a SLEDAI-2K score of ≥ 6 at the Screening Visit and a clinical SLEDAI (excluding laboratory results) score ≥ 4 at the Screening and Randomization Visits. Points for arthritis and/or rash must be present at both the Screening and Randomization Visits.
 7. Subjects must have moderate to severe rash and/or arthritis as demonstrated by BILAG-2004 score A or B in the in the mucocutaneous and/or musculoskeletal body systems at both Screening and Randomization Visits.
 8. A documented history of positive antinuclear antibody (ANA)
OR
A screening result of positive ANA test by immunofluorescent assay (IFA) with titer $\geq 1:80$ or an equivalent assay
OR
A documented history or positive screening result of elevated anti-dsDNA or ENA antibodies (e.g., anti-Smith, SSA, SSB, RNP).

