 9. Subjects must have been on prednisone (or prednisone equivalent) for ≥ 8 weeks prior to the Screening Visit and on a stable dose of 7.5 mg to 30 mg of prednisone (or prednisone equivalent) for ≥ 4 weeks prior to the Screening Visit.
 10. Subjects must have a mean systolic blood pressure ≤ 150 mm Hg and a diastolic blood pressure of ≤ 90 mm Hg determined by the average of 3 seated readings taken at least 5 minutes apart at the Screening and Randomization Visits.
 11. Subjects using antimalarials and NSAIDs must have been on a stable dose for at least 4 weeks prior to the Screening Visit and remain on that dose throughout the study.
 12. Subjects using methotrexate, azathioprine and/or mycophenolate mofetil must have been a stable dose for at least 8 weeks prior to the Screening Visit and remain on that dose throughout the study.
 13. Subjects must be able to communicate effectively with study personnel.
 14. Subjects must be able and willing to follow all protocol requirements and study restrictions.
 15. Subjects must be able and willing to return for all study visits.

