 - Any known history of scleroderma, osteoporosis, or ocular herpes simplex. For the purposes of this study, osteoporosis is defined as evidence of vertebral or long bone fracture, or lumbar T-score > 2.0 SD below the mean of the reference population.
 - Any primary adrenocortical insufficiency, or adrenal cortical hyperfunction.
 - Any current congestive heart failure (defined as New York Heart Association Functional Class III to IV).
 - Peptic ulcer (within 24 weeks prior to the Screening Visit).
 - Recent major surgery (within 24 weeks prior to the Screening Visit).
13. Subject has a history of chronic active hepatitis including active or chronic hepatitis B, or acute or chronic hepatitis C. Subjects must have negative Hepatitis B surface antigen (HBsAg) or Hepatitis B core antibody (HBcAb) and negative Hepatitis C virus antibody (HCV) or HCV polymerase chain reaction (PCR) < 25 IU/mL (HCV PCR will be automatically analyzed if HCV is positive) at the Screening Visit.
14. Subject has a history of tuberculosis (TB) infection, any signs/symptoms of TB, or any close contact with an individual with an active TB infection. Subjects must not have a positive or indeterminate interferon gamma release assay (IGRA) for TB at the Screening Visit.
15. Subject has a clinically significant infection requiring administration of IV antibiotics or hospitalization in the 4 weeks prior to the Screening Visit or between the Screening Visit and the first dose of study drug.
16. Subject has known immune compromised status (not related to SLE or therapies for SLE), including but not limited to, individuals who have undergone organ transplantation or who are known to be positive for the human immunodeficiency virus.
17. Subject has any solid tumor malignancy currently diagnosed or undergoing therapy, or has received therapy for any solid tumor malignancy in the 5 years prior to the Screening Visit; with the exception of treated and cured basal cell carcinoma, treated and cured squamous cell carcinoma of the skin, and treated and cured carcinoma in situ of the cervix.

18. Subject has a diagnosis of, is undergoing therapy for, or has received therapy for a hematologic malignancy in the 5 years prior to the Screening Visit.

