13.3 Screen Failure

Subjects will be allowed to repeat any single screening assessment/procedure once, if necessary, if it is within the screening window. The subject will not be considered a screen failure unless the repeat assessment/procedure results do not meet eligibility criteria. The period from starting screening related procedures at the Screening Visit to the Randomization Visit must not exceed 28 days, inclusive of any repeat screening procedures.

Subjects who do not meet all of the eligibility criteria at the Screening or Randomization Visits will be deemed a screen failure and the reason for the screen failure will be documented. A subject who is a screen failure at the Screening or Randomization Visit may be rescreened. The subject must repeat all screening procedures. The period from the start of rescreening related procedures to the first dose of study drug must not exceed 28 days. Subjects may be rescreened only once.

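### Exclusion 13 and section 19.7 set different hepatitis B entry rules; as a minor point, section 19.6 restates the blood pressure rule incompletely

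*Combined protocol and SAP*

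**What the plan says.** **Hepatitis B.** Exclusion 13 in section 13.2 has two sentences. The first bars a history of chronic active hepatitis, and it names active or chronic hepatitis B. The second sets the laboratory condition at Screening: "Subjects must have negative Hepatitis B surface antigen (HBsAg) or Hepatitis B core antibody (HBcAb"). Section 19.7 has both tests done at Screening and continues: "Results of these tests must be negative or nonreactive for subjects to qualify for the study". The synopsis lists a history of hepatitis among the exclusions without further definition.

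**Hepatitis C.** The same sentence of exclusion 13 asks for "negative Hepatitis C virus antibody (HCV) or HCV polymerase chain reaction (PCR) < 25 IU/mL". Section 19.7 has a positive antibody trigger the PCR and adds: "HCV PCR must be < 25 IU/mL to qualify for the study".

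**Blood pressure.** Inclusion 10 in section 13.1 states: "Subjects must have a mean systolic blood pressure ≤ 150 mm Hg and a diastolic blood pressure of ≤ 90 mm Hg", taken as the average of three seated readings at Screening and Randomization. Section 19.6, under its Screening/Randomization text, describes the subject who does not qualify: "A subject with systolic blood pressure > 150 mm Hg and diastolic blood pressure > 90 mm Hg (average of 3 assessments").

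**What governs entry.** Section 13.1 opens with "Subjects must meet all of the following criteria for inclusion in the study at the Screening Visit and the Randomization Visit". Section 13.3 adds "Subjects who do not meet all of the eligibility criteria at the Screening or Randomization Visits will be deemed a screen failure". Section 16.1.2 lets only subjects who satisfy every eligibility criterion be randomized.

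**The concern.** A site that screens hepatitis B against section 13.2 alone can pass a subject whom section 19.7 bars. A site that follows 19.7 will turn the same subject away. About 60 sites are planned (section 12.3), so entry could differ between sites. The rule is a safety gate in subjects who take 7.5 to 30 mg of prednisone or equivalent a day and may also take methotrexate, azathioprine or mycophenolate mofetil. The visible part of Table 8-1 has hepatitis serology at Screening only, so no later scheduled test that can be seen would pick up the difference.

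There is a smaller consequence for the analysis sets. Whether such a subject is an entry deviation depends on which section is applied. If it were classed as a major deviation, the subject would leave the Per-Protocol Population (section 21.2).

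For blood pressure, the 19.6 sentence sits beside the instructions for taking the three readings, so staff may use it as a checklist. Raised blood pressure is a listed reaction to the drug (section 10.5). Read on its own, the sentence does not flag a subject with only one component above the limit.

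**Working it through.** No stated figure is at issue. The check sets each pair of rules side by side and applies both to every possible outcome.

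**Hepatitis B.** As written, the laboratory sentence of exclusion 13 accepts a subject if HBsAg is negative *or* HBcAb is negative. Section 19.7 accepts a subject only if both are negative.

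| HBsAg | HBcAb | Exclusion 13, laboratory sentence | Section 19.7 |
|---|---|---|---|
| negative | negative | accepts | accepts |
| negative | positive | accepts | bars |
| positive | negative | accepts | bars |
| positive | positive | bars | bars |

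The rules differ in 2 of 4 rows. In the third row, a surface-antigen-positive subject with active or chronic hepatitis B is already barred by the first sentence of exclusion 13. That leaves the second row as the practical conflict.

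**Does the all-criteria requirement settle it?** Sections 13.1, 13.3 and 16.1.2 enforce the listed criteria. The listed hepatitis B criterion is exclusion 13, which is the looser text. A subject in the second row therefore meets the criteria as listed. The stricter condition comes only from 19.7's own statement that negative results are needed to qualify.

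**Hepatitis C.** There are three outcomes: antibody negative; antibody positive with PCR below 25 IU/mL; antibody positive with PCR at or above 25 IU/mL. Both sections accept the first two and bar the third, so they agree in 3 of 3. The 'or' in this half is deliberate and correct.

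**Blood pressure.** Inclusion 10 passes a subject if the mean systolic is at most 150 and the diastolic at most 90. The 19.6 sentence names a subject as not qualifying if systolic exceeds 150 and diastolic exceeds 90.

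| Example | Inclusion 10 | Named by 19.6 as not qualifying |
|---|---|---|
| 150/90 | passes | no |
| 160/85 | fails | no |
| 140/95 | fails | no |
| 160/95 | fails | yes |

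Inclusion 10 fails three of the four states and 19.6 names one of those three. The two are logically compatible, because 19.6 says who does not qualify and is silent on who does. Here the stricter text is itself a listed criterion, so the all-criteria requirement does settle the matter.

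The fractions count outcome states, not subjects. Rare and common states carry the same weight.

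**The case against.** The best defence on hepatitis B is that exclusion 13 is only loosely drafted and the intent is plain. Section 19.7 says outright that the results must be negative to qualify, and the synopsis excludes a history of hepatitis in broader terms than the first sentence of exclusion 13. Both point to the strict rule, and that stands as evidence of intent. It is not conclusive. A positive core antibody is not the same as a recorded history, and the hepatitis C half of the same sentence uses 'or' permissively and correctly, which gives a reader reason to take the hepatitis B 'or' literally as well.

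A reader might also infer that the stricter hepatitis B rule prevails because every criterion must be met. The documents do not support that step: the looser wording is the criterion, and the stricter wording is in the laboratory procedures.

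On blood pressure, the defence largely succeeds. The criteria are reviewed at both Screening and Randomization (Table 8-1; sections 15.1 and 15.2), and a subject at 160/85 or 140/95 fails at that review. A reader might infer that 19.6 contradicts inclusion 10 or admits such subjects. It does neither; it is an incomplete restatement.

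It is also tempting to treat the on-study definitions as errors. The 19.6 recording prompt, the event of special interest (section 22.5) and the accelerated hypertension threshold (section 16.3.1) each need both components raised, so a reading of 195/85 meets none of them. These are definitional choices. A one-component rise can still be recorded as an ordinary adverse event and counted by arm (section 21.8.1), and the last item of 16.3.1 allows it to lead to stopping treatment. Vital signs are also summarized by visit and arm (section 21.8.3).

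**Conclusion.** The hepatitis B wording is wrong as it stands: two operative sections give different answers for a subject who is HBsAg-negative and HBcAb-positive, and nothing in the documents reconciles them. This should be corrected. Narrowing the conflict to that one result pair assumes that a surface-antigen-positive subject would be judged to have active or chronic hepatitis B under the first sentence of exclusion 13.

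The blood pressure point is minor and editorial.

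The size is limited. No sample size, power or significance figure changes. The primary mITT set is defined by randomization, dosing and post-baseline efficacy data, so it does not depend on either wording. The documents give no frequency of core-antibody positivity or of isolated systolic or diastolic elevation, so no count of affected subjects can be offered. A reader might infer that the efficacy comparison is biased; nothing in the documents supports that.

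**What to change.** 1. **Hepatitis B (main change).** In exclusion 13, require HBsAg *and* HBcAb to be negative, which matches 19.7. If the sponsor does intend to admit core-antibody-positive subjects, amend 19.7 to say so instead. Leave the hepatitis C wording unchanged in both places.
2. **Blood pressure (editorial).** In the 19.6 entry sentence, change 'and' to 'or', so that either component above its limit disqualifies, as in inclusion 10.
3. **Eligibility check.** Program the single agreed rule for each item.

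The cost is two short wording changes in an amendment and one eligibility edit check.

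Optional, as an improvement and not a correction: add one Safety Population table by arm of subjects with any on-study systolic pressure of at least 180 or diastolic pressure of at least 100 mm Hg, unless the statistical analysis plan referred to in section 21.6 or a redacted section already has it. It uses vital signs already collected, so it would also count rises that no investigator recorded as an adverse event. The existing on-study definitions can stay as they are.
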